- 5) Currently enrolled in any investigational study in which the subject is receiving any type of drug, biological, or non-drug therapy.
- 6) Use of oral, topical analgesics, or other medications known to interfere with itch or pain perception 48 hours prior to the study visits (e.g. antihistamines, anesthetics, anti-inflammatories, opioids, neuroleptics, etc.).

- 7) Use of emollients on the volar aspects of the forearms arms on the day of the study visit.
- 8) Use of anti-depressants, anti-psychotics, and illicit drugs.
- 9) Known history of neuropathy, uremia, uncontrolled thyroid disease, and diabetes mellitus.
- 10) Known history of anaphylactic shock, or allergy to cowhage and/or known adverse reactions to lidocaine (or other local anesthetics of the amide type), ketamine or amitriptyline.
- 11) Pregnant (females of childbearing potential will undergo an hCG pregnancy test).
- 12) Currently incarcerated.

6) Number of Subjects*

A priori power calculations were conducted in G*Power based on data from a previous test-retest study³⁸. In order to have an effect 80% power with a size effect of 0.30 and alpha error probability of 0.05, we will need 36 subjects (10 within post hoc pairwise comparisons). We estimate that we will need to screen up to 42 individuals in order to enroll 36 healthy subjects.

We will seek to recruit a sample with an approximately equal gender distribution.

7) Study-Wide Recruitment Methods*

IRB approved flyers will also be placed around the University of Miami medical campus, and within the waiting rooms of the Department of Dermatology Out Patient Clinic at UMH (South Building, suites K-M) and at the Lennar Foundation Medical Center.

8) Study Timelines*

This projected is expected to last 8 months. The first 6 months will be dedicated to subject enrollment. During this time each subject will be a part of 2 study visits; one session lasting approximately 2.75 hours and one lasting approximately 2 hours. The second session must be completed within 7 days of the first session. The second 2 months will be dedicated to the sample analysis and the last month will be dedicated to dissemination of findings.

9) **Study Endpoints***

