The primary endpoints are visual analog scale (VAS) ratings of the perceived intensity of itch sensation elicited by epicutaneous application of cowhage spicules (non-histaminergic itch) on the volar aspects of the forearms comparing skin pretreated with vehicle cream with the KeAmLi-combination. Ratings will be plotted vs. time to generate a temporal itch intensity graph and the area under the curve (AUC) will be calculated for each subject. The secondary study endpoints are the individual itch peak intensity, itch peak time, and itch time duration comparing skin pretreated with vehicle cream with ketamine, amitriptyline, lidocaine, and KeAmLi-combination.

The exploratory outcomes (for all experimental interventions vs. the vehicle condition) are:

- Warmth detection threshold (°C needed to perceive warmth sensation)
- Heat pain threshold (°C needed to perceive heat pain)
- Mechanical detection threshold (mN needed to perceive touch)
- Mechanical pain threshold (mN needed to perceive pain)
- Development of hyperknesis (NRS ratings of itch evoked by touch before vs. after cowhage provocation)

10) **Procedures Involved***

At the beginning of the first session, subjects will be asked to fill out an informed consent, and a form for demographic information including health information. They will also be asked if they have taken any allergy or pain medicine during the past 24 hours. If so they will be asked to come back at a later time since these drugs might interfere with the study. Females of childbearing potential will undergo an hCG pregnancy test. Finally, subjects will receive instruction on the use of the visual analog scale for rating the intensity of itch sensation. Below is a short procedural overview of the proposed study this is followed by sections introducing in details each of the methods applied.

Subjects will be seated comfortably in a chair with both arms resting on armrests or on a pillow. Using a block-randomized design, we will deliver either topical vehicle (PCCA Lipoderm[®]), topical ketamine 10%, topical amitriptyline 5%, lidocaine 5% or KeAmLi-combo (ketamine 10%, amitriptyline 5%, and lidocaine 5%) to four 4 x 4 cm predefined skin areas on the ventral forearms over two study visits. The 1st visit will involve applying 3 of the 5 treatments (randomized), to 3 of the 4 designated test sites in a randomized manner. The 2nd visit will involve applying the

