remaining 2 treatments to 2 of the 4 designated test sites in a randomized manner. The subject and investigator will be blinded to the identities of the treatments (see blinding procedure below).

Application will be conducted with the investigator wearing nitrile gloves. The pre-treatment will occur under topical occlusion for 30 minutes to allow the ointment to be adsorbed. Following this, residual ointment will be removed and sensory testing, strictly within the pretreated area, will commence. For each of the five tested topical solutions the following procedures will be conducted (see also Fig. 1):

- 1) Demarcation of 4 x 4 cm treatment area (see Fig. 2)
 - a) Application of 2 g of ointment (randomized substance)
 - i) 30 min pretreatment
 - (1) During this time a subject familiarization procedure for the quantitative sensory testing will be conducted
 - ii) Removal of residual ointment
 - iii) Local safety assessment
- 2) Thermal sensory thresholds
 - a) HDT
 - b) HPT
- 3) Mechanical sensory thresholds
 - a) MDT
 - b) MPT
- 4) Baseline sensitivity to touch-evoked itch (STI) assessment
- 5) Cowhage provocation
 - a) 40-45 spicules rubbed into the epidermis
 - b) Continuous VAS-recording of itch and pain for up to 15 minutes
- 6) Post-provocation STI assessment (assessment of hyperknesis)
 - a) Spicules gently removed by 2-3 tape-strippings
 - i) 0
- 7) Procedure is repeated with next topical intervention

The second session is conducted in a manner completely identical to session 1. However, the remaining 2 ointments not used in session 1 are assessed in the second session. The second session must be completed within 7 days of the first session.

[figure not shown]

Figure 1 – Overview of the course of study procedures. Grey boxes in the top designate inclusion of subjects for sensory and skin parameters assessment in the depicted test-battery below. Thermal and mechanical sensitivity quantitative sensory tests are performed first, then assessment of STI is assessed and the itch provocation is conducted. Times estimates are derived from the DFNS protocol³⁹ and may vary between subjects mainly due to differences in the ease of understanding instructions. Abbreviations: WDT = warmth detection threshold; HPT = heat pain threshold; MDT = mechanical detection threshold, MPT = mechanical pain threshold; NRS = numeric rating scale; STI = Sensitivity to Touch-evoked Itch; VAS = visual analog scale;

[figure not shown]

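### Exclusion 6 bars interfering medicines for 48 hours before the visits, but the only timed question described looks back 24 hours, so last use 24 to 48 hours earlier passes it

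*Combined protocol and SAP*

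**What the plan says.** Section 5, exclusion 6, covers oral and topical analgesics and "other medications known to interfere with itch or pain perception 48 hours prior to the study visits". Its examples are "e.g. antihistamines, anesthetics, anti-inflammatories, opioids, neuroleptics, etc". The word for visits is plural, so the criterion applies to each of the two visits.

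Section 10 opens with the entry procedures: "At the beginning of the first session, subjects will be asked to fill out an informed consent", together with a form for demographic and health information. Subjects are then "asked if they have taken any allergy or pain medicine during the past 24 hours". The consequence of a yes is deferral: "If so they will be asked to come back at a later time since these drugs might interfere with the study".

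On the other visit, Section 10 says: "The second session is conducted in a manner completely identical to session 1". It then sets out the remaining two ointments and the 7-day limit, without mentioning the medication question.

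Three of the five treatments are allocated at random to visit 1 and the other two to visit 2. The primary endpoint (Section 9) is the area under the itch VAS curve, vehicle against KeAmLi, in 36 subjects (Section 6).

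**The concern.** The question at the door does not enforce the criterion. It covers half of the excluded period, and its wording (medicine for allergy or pain) differs from the list in exclusion 6. It is also tied to the first session, while the criterion applies to both.

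The drugs concerned are ones the protocol itself expects to disturb itch and pain ratings. Those ratings supply the primary endpoint, the secondary itch measures and most of the exploratory outcomes. A within-subject comparison protects against this only when the two creams being compared are tested under the same conditions. With treatments spread over two visits up to a week apart, medicine taken before one visit can reach vehicle and not KeAmLi, or the reverse.

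The statistical analysis text in Section 10 would not reveal the problem. It names no medication covariate, no visit term and no rule for a subject later found to have broken exclusion 6.

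**Working it through.** **1. The two windows side by side.**

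| | Exclusion 6 (Section 5) | Entry question (Section 10) |
|---|---|---|
| Look-back | 48 h | 24 h |
| Medicines | analgesics and a list of interfering classes | allergy or pain medicine |
| Visits | both | written for the first |
| If positive | excluded | deferred |

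Uncovered period: 48 − 24 = 24 h, half of the excluded window. Last use within 24 h is caught if the subject counts the drug as allergy or pain medicine. Last use more than 48 h earlier is allowed by both texts. Last use between 24 and 48 h is barred by one and passed by the other.

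**2. How often the primary comparison is split across visits.** Assume all 3 + 2 splits are equally likely. Section 10 says block-randomised but gives no scheme.

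- All splits: C(5,3) = 10.
- Vehicle and KeAmLi both at visit 1: C(3,1) = 3.
- Both at visit 2: C(3,3) = 1.
- Vehicle at visit 1, KeAmLi at visit 2: C(3,2) = 3.
- KeAmLi at visit 1, vehicle at visit 2: C(3,2) = 3.

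They are apart in 6 of 10 (60%), and the two directions are balanced, 3 against 3.

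**3. Subjects affected.** The documents give no rate of use, so the rate r is assumed: the share of subjects who used an interfering drug in the uncovered period before exactly one visit. Affected primary differences = r × 0.60 × 36.

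- r = 5%: 1.1 subjects
- r = 10%: 2.2 subjects
- r = 20%: 4.3 subjects

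**4. Noise.** Suppose each affected difference is shifted by d standard deviations of the paired difference, in random direction. The variance rises by a factor of 1 + (r × 0.60) × d², and the standard error by its square root. With r = 10% (6% affected):

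- d = 0.5: 1 + 0.06 × 0.25 = 1.015; standard error up 0.7%
- d = 1: 1 + 0.06 × 1 = 1.06; standard error up 3.0%

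With r = 20% and d = 1: 1 + 0.12 = 1.12; standard error up 5.8%. The values of d are assumptions too.

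**5. Dilution.** If the drug cuts itch by a fraction f at one visit, each cream is affected when it falls on that visit: probability 3/5 for visit 1 and 2/5 for visit 2. Averaged over the randomisation, that subject's expected difference is multiplied by 1 − 0.6f or 1 − 0.4f. Over the sample the mean difference shrinks by at most r × 0.6 × f. Even with f = 1 (itch abolished), this is 3%, 6% and 12% for r = 5%, 10% and 20%. These are ceilings. A smaller residual effect scales them down, and the documents give no value for f.

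**The case against.** The strongest reply is that the mismatch is real but its effect is small and not demonstrated. Several parts of that reply stand.

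- **Other screening may exist.** Subjects fill out a form with health information, and Section 6 foresees screening up to 42 people to enrol 36. Exclusions 8 to 10 also have no question of their own in Section 10, so some screening must happen outside the procedures written there. A reader might infer that the 24-hour question is the only safeguard. The documents do not establish that. They support only that no 48-hour check is described.
- **Drug classes.** A reader might infer that users of neuroleptics slip through. Exclusion 8 separately bars anti-psychotics, with no time limit, and in lay terms most of the remaining classes are medicines for allergy or pain. What is left is two texts that should use one list.
- **Visit 2.** A reader might infer that nothing is asked at visit 2. The sentence "The second session is conducted in a manner completely identical to session 1" may carry the question over. But the question stands beside informed consent, which would not naturally be repeated, so the point is unclear rather than settled either way. If it is carried over, it is still a 24-hour question.
- **Direction.** A reader might infer that the treatment effect is biased in favour of one cream. Random allocation to visits makes medicine use as likely to fall on vehicle as on KeAmLi, and the count of splits above shows that balance, so this reading fails.
- **Residual effect.** Cowhage is described as a non-histaminergic model, and nothing in the documents shows that an antihistamine taken more than 24 hours earlier changes cowhage itch. This limits any claim about size. It does not remove the contradiction, because exclusion 6 lists antihistamines among the barred drugs.

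The reply does not resolve the two windows. Reading the 24-hour question as a same-day deferral check on top of the criterion is possible, but no text says so.

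**Conclusion.** The point holds in a limited form. Sections 5 and 10 contradict each other on the look-back window. As written, a subject whose last use was 24 to 48 hours before a visit meets an exclusion criterion and passes the only timed check described. That conclusion rests on the text alone and is firm.

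The consequence for the primary analysis is less certain and probably modest: about 1 to 4 of 36 primary differences affected for assumed use of 5% to 20%, appearing as noise and dilution. This rests on equally likely splits, an assumed rate of use and an assumed residual drug effect, none of which the documents supply. The mismatch deserves correction because it decides who is tested and is cheap to repair, not because it has been shown to endanger the result. The documents do not show which of the two windows was intended, and this review takes no position on that.

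**What to change.** Reconcile exclusion 6 in Section 5 with the entry question in Section 10, so that both carry one look-back window and one list of drug classes. The sponsor decides which. State in Section 10 that the question is asked, and the answer recorded, at the start of both visits, and that a positive answer leads to the deferral the plan already has.

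The cost is one sentence in Section 10, one line on the visit form and possibly a few rescheduled visits. A deferred second visit must still fall within 7 days of the first, so it helps to schedule visit 2 with some slack.

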Figure 2 – Overview of application areas on the volar forearms. Notice that this is an exemplification. Actual substance application/familiarization will be randomized for order, and location. In session 1, only three of the four areas will be used. In session 2, only two of the four areas marked for substance application will be used.

Computerized Visual Analog Scale (VAS) Scoring: During induction of itch the subjects will be asked to rate the sensation of itch, stinging/pricking and burning on a VAS scale from 0-10 where 0 denotes “no itch” and 10 denotes “worst imaginable itch” and similarly for sensations of stinging/pricking and burning, both of which are frequently associated with the sensation of itch. The subjects will report the sensation using a horizontal electronic scroll bar giving a digital output in a frequent (i.e., every 15 seconds) discrete manner. Rating of the itch intensity will continue until ≥ 3 subsequent ratings are below 1 (assessed for itch) or after a maximum duration of 15 minutes. Based on similar studies this is typically between 5-15 minutes after the itch has been induced. Nociceptive sensations associated with non-histaminergic itch are usually subtle; typically rated 1-3 on a 0-10 VAS and “weak” on a generalized Labeled Magnitude Scale (gLMS)^{38,40,41}.

Itch scores are typically rated 3-8 on a 0-10 VAS scale and “moderate” to “strong” on a gLMS (depending on induction paradigm).

Application of cowhage spicules: Each 4 x 4 cm test area on the forearm will undergo itch induction with cowhage after a 5-minute rest from the thermal testing. Ratings of itch intensity will be taken on a VAS scale (0-10) continuously for 10 minutes. Subjects will be asked to not scratch the areas.

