Statistical Analysis: Data will be entered into a database program, such as Microsoft Excel and/or IBM SPSS, and analyzed at using Prism GraphPad 6 and/or IBM SPSS. Basic descriptive statistics using mean (SEM), range, and n (%) will be calculated in Excel and presented. Statistical significance will be set at $p < 0.05$. Analysis will be performed within and between groups.

Normality assessment will be tested by visual inspection and Shapiro-Wilks tests. A repeated measure (between–within) ANOVA will be used for the main analysis and post hoc comparisons will be conducted using the Bonferroni correction in a manner similar to Dunnett’s test.

Blinding procedures: The study will be conducted under double-blinded conditions. The investigators responsible for the data collection, i.e. application, sensory tests, itch provocations, and data entry, will be blinded to the substance being applied. Blinding will be carried out by random allocation of letters “A” to “E” to labels on the pharmaceuticals (including the vehicle). This task is carried out at the compounding pharmacy. With delivery of the pharmaceuticals a list specifying the compounds corresponding to allocated letters is supplied to the PI. In case of serious adverse effects, the PI will breach the blinding. Otherwise unblinding will not occur until after the primary analysis has been conducted.

Local safety assessment: After pretreatment with each ointment (before any sensory testing is performed), and after each cowhage application a local safety assessment will be done. Erythema, edema, and any other local reaction will be recorded on a 5-point Likert scale (0=clear, 1=almost clear, 2=mild, 3=moderate, 4=severe).

11) **Data Management***

All of the data, including records of subjects, source documents, and informed consent will be kept in the study center office under lock for 6 years after the study finished. The study center office is located at: [name].

12) **Provisions to Monitor the Data to Ensure the Safety of Subjects***

The study team will be responsible for protecting the safety, rights, and well-being of study participants. When testing is performed the subjects' vital signs (blood pressure, heart rate, and respiratory rate) will be monitored.

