2. **Cowhage application.** No specific serious risks or adverse effects are associated with the application of cowhage spicules to the skin. At the site of application, subjects may experience a mild to moderate burning/stinging sensation apart from the itch sensation itself, which may last from 1-7 minutes^{40,41,45}. Cowhage is not an allergen and does not cause contact dermatitis, chemical irritation or erythema. No serious adverse reactions to cutaneous cowhage application have been described in the literature. We do not expect a tachyphylactic reaction or an additive

affect from multiple cowhage applications because we are not applying cowhage more than once to the same location during the same study visit. In the event of an allergic reaction, the study will be stopped and appropriate treatment administered (use of EpiPen).

Following use of EpiPen, the patient will be referred to the emergency room, where basic vitals including heart rate, blood pressure, and oxygen saturation in the blood will be monitored. A respiratory exam will also be given to assess the quality of breathing. Steroids to prevent additional airway closure and fluids to maintain blood pressure will be given as necessary. The patient will be monitored in the emergency room for 6 hours, and then sent home with an additional EpiPen to guarantee immediate access to self-injectable epinephrine. The patient will be instructed on EpiPen usage. The patient will also be educated to watch for symptoms of biphasic anaphylaxis, which may occur up to 72 hours after initial symptoms of anaphylaxis.

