Once it reaches the lab, [name] staff documents on the tube the date of arrival. This batch is labeled the “master batch”. The tube of cowhage is then stored under dry conditions in a 4°C refrigerator. Also

upon arrival, the spicules are examined under a microscope to confirm the material is cowhage. The dimensions of the spicules (2-4 mm length, 1-3 µm tip diameter) are measured⁴⁰.

The investigator then tests the spicules for the itch induction ability with the same application method used in studies⁵⁷. Forty to forty-five spicules (a dose found to induce a consistent and reproducible itch sensation) are counted under the microscope and then rubbed in to a 4x4 cm area on the volar forearm for 45 seconds in a circular motion. Approximately 0.2 mm of the spicule tip enters the skin. Forty-five spicules of cowhage are equivalent to 45 µg of material, containing about 90-140 ng of mucunain⁴⁵. The spicules usually induce itch after ~30-90 seconds of the application. If 2 minutes pass without itch being induced, the spicules are deemed inactive and the batch will not be used for itch induction in studies. If itch is induced, the itch sensation will last ~7 minutes and itch intensity is rated using a 0-10 numerical rating scale (NRS) every 30 seconds until the itching subsides. Cowhage spicules are removed from the skin using tape, which is disposed of in a biohazard trash bin. The itch subsides quickly once the spicules have been removed. Itch is only felt at the site of induction and mild temporary erythema at the induction site is common.

For studies using cowhage to induce itch, a small portion of the master batch of cowhage is aliquoted into smaller 5 ml tubes as a “working batch”. The date of separation from the main batch is marked on the smaller tube. This tube then remains at room temperature for the duration of the study. The potency of the cowhage is preserved for many years when stored in a dehumidified area at room temperature or at 4°C, but the potency is checked every 3 months and before the start of any study.

Drug Formula for Ketamine 10% - Amitriptyline 5% - Lidocaine 5% (Per 100gm of cream)

- Ketamine HCl (Fagron Pharmaceuticals NDC 51552-0697-07): 10grams
- Amitriptyline HCl (Medisca NDC 38779-0189-09): 5 grams
- Lidocaine HCl (Medisca NDC 38779-0082-03): 5 grams
- Ethoxy Diglycol (Fagron Pharmaceuticals NDC 38779-1903-07): 5mL
- Liquigel (Medisca NDC 38779-2531-01): 3 grams
- Lipoderm Cream Base (PCCA NDC 51927-3338-00): 72 grams

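### Five treatments share four skin areas, so every completer reuses at least one; always using the untouched area at visit 2 would limit this at almost no cost

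*Combined protocol and SAP*

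**What the plan says.** Section 10 (Procedures Involved) assigns the five creams "to four 4 x 4 cm predefined skin areas on the ventral forearms over two study visits". Visit 1 applies three of them to three of the four areas. Visit 2 applies the "remaining 2 treatments to 2 of the 4 designated test sites in a randomized manner". The Figure 2 legend repeats both counts and says that order and location are randomized; for the second visit it states: "In session 2, only two of the four areas marked for substance application will be used".

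Each cream brings the full sequence to its area: 30 minutes under occlusion, sensory tests, 40 to 45 cowhage spicules, and removal by two or three tape-strips. On timing, the same section says: "The second session must be completed within 7 days of the first session". No minimum interval is given.

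Section 14 (Risks to Subjects, item 2) expects no tachyphylaxis or additive effect from repeated cowhage "because we are not applying cowhage more than once to the same location during the same study visit". The Statistical Analysis paragraph of Section 10 says a repeated-measures "ANOVA will be used for the main analysis and post hoc comparisons will be conducted using the Bonferroni correction". It names no term for visit, area or prior use of an area.

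**The concern.** The primary comparison is within subject: itch AUC on vehicle-treated skin against AUC on KeAmLi-treated skin. It is cleanest when both areas are in the same state. With four areas for five applications that cannot always be so, because some visit-2 applications must go on skin that was treated and provoked a few days before.

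The plan regards repeat provocation of one location as worth a comment in Section 14, but the comment stops at a single visit, and the design forces repetition between visits. The plan also leaves visit-2 placement fully random over the four areas, so a second reused area, which is never necessary, occurs by chance. At stake are the precision of the primary contrast and, if a cream's effect lasted until visit 2, a small shift in its mean.

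**Working it through.** The plan gives no figure on this point, so there is none to reproduce.

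**Inputs.** Four areas, three used at visit 1 and two at visit 2 (Section 10 and Figure 2 legend); five treatments, each given once (Section 10); 36 subjects (Section 6). Assumptions: all 36 complete, and treatments and areas are allocated with equal probability, since the block structure is not described.

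**Forced reuse.** Minimum overlap = 3 + 2 − 4 = 1. The two visit-2 areas include the untouched one with probability 2/4 = 0.5. So half of completers have one reused area and half have two; the mean is 1.5.

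**Primary pair.** A given cream falls at visit 2 with probability 2/5 = 0.4, and its area has then been used before with probability 3/4. Vehicle and KeAmLi both fall at visit 2 with probability 1/10, and both are then on reused skin with probability 1/2. If the untouched area is always used at visit 2, exactly one of the two visit-2 creams is on reused skin.

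| Quantity | As planned | Untouched area always used at visit 2 |
|---|---|---|
| Reused areas per completer | 1 or 2, mean 1.5 | 1 |
| Vehicle on reused skin (same for KeAmLi) | 0.4 × 0.75 = 0.30 | 0.4 × 0.5 = 0.20 |
| Both on reused skin | 0.1 × 0.5 = 0.05 | 0 |
| Exactly one | 0.30 + 0.30 − 2 × 0.05 = 0.50 (18 of 36) | 0.20 + 0.20 = 0.40 (14.4 of 36) |
| At least one | 0.55 | 0.40 |
| Visit-2 observations, reused / untouched (of 72) | 54 / 18 | 36 / 36 |

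With five distinct areas every reuse entry is 0. Full enumeration of the 10 × 24 × 12 = 2,880 layouts as planned, and of the 10 × 24 × 6 = 1,440 constrained layouts, gives the same probabilities.

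**Noise.** Suppose prior use shifts AUC by s equally under both creams. The mean shift in the contrast is 0. The per-subject difference in prior use is +1 or −1 with total probability 0.50, so the SD added to the mean difference is s × √(0.50/36) = 0.118s. With the constraint it is s × √(0.40/36) = 0.105s. To set this against ordinary variability, let σ be the within-subject SD of one AUC. The variance of the mean difference rises from 2σ²/36 by 0.5s²/36, a relative increase of 0.25(s/σ)². For assumed s/σ of 0.3 and 0.5, that is 2.25% and 6.25% in variance, or about 1% and 3% in standard error.

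**Possible dilution.** Suppose an active cream at visit 1 lowers a later AUC on the same area by r (unknown, possibly 0). Vehicle on reused skin always follows an active cream: 0.30. KeAmLi on reused skin follows an active cream in three cases of four: 0.30 × 3/4 = 0.225.

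- If the lowering is the same under both creams, the contrast shrinks by 0.30r − 0.225r = 0.075r.
- If there is no further lowering under KeAmLi, it shrinks by 0.30r.
- With the constraint the range is 0.20r − 0.15r = 0.05r up to 0.20r.

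As illustration only, r of 10% of AUC gives 0.75% to 3% of AUC as planned, and r of 20% gives 1.5% to 6%.

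**The case against.** The strongest reply is that randomization already deals with this. Treatments and locations are randomized, so prior use is equally likely under vehicle and KeAmLi, and an equal effect cancels. The remaining noise is part of the observed variance of the within-subject differences, so the test already allows for it. On the assumptions above it costs only a few percent in standard error. This stands, and it is why the point is minor.

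It can also be said that nothing in the documents shows an effect lasting until visit 2. Application is for 30 minutes, residual cream is removed, and Section 28 says of cowhage: "The itch subsides quickly once the spicules have been removed". The Section 14 sentence is a risk statement and true as written; it is not offered as a statistical defence of the layout. The power calculation rests on a test-retest study that cannot be seen here. All of that stands. It does not explain why a second reused area should be left to chance when a constraint on the list prevents it.

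A reader might infer two stronger points that the documents do not support:

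- **The 48-hour criterion.** Exclusion 6 bars "Use of oral, topical analgesics, or other medications known to interfere with itch or pain perception 48 hours prior to the study visits", which could be read as a washout that the study's own creams may breach. It sits in an eligibility list and reads as concerning the subject's own medication. Applied to study creams, it would equally bar the three creams tested together at visit 1. Nor is it specific to reused areas.
- **Tape-stripping.** One might suppose that earlier stripping raises later uptake of cream and so enlarges the contrast. No section says so.

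**Conclusion.** The point holds in a limited form. Reuse of at least one area per completer is certain from the plan's own counts, and no section addresses reuse between visits. On average half of completers also have a second, avoidable reused area, if allocation is equal-probability.

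The consequence for the primary contrast is modest: added noise of 0.118s, already reflected in the observed variance, and a dilution of 0.075r to 0.30r only if drug effect persists on the same area. Neither s nor r can be obtained from the documents, and either may be zero. Under the residual-drug assumption the shift is toward no difference, so it would not create a false positive. A reader might take the forced reuse as showing that the primary comparison is biased; the documents do not support that. Severity: minor. The case for acting is that the main remedy is practically free.

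**What to change.** 1. **Allocation list.** Require that visit 2 always includes the untouched fourth area. Choose at random which of the two remaining treatments goes on it, and at random which used area takes the other. Reuse falls to one area per completer. Cost: the constraint on the list; visits, creams, labelling and tests do not change.
2. **Five areas, if they fit.** A fifth 4 x 4 cm volar area, with the five treatments randomized to distinct areas, removes reuse altogether. It needs a new site template and splits areas unevenly between forearms. Figure 2 is not shown and its legend also mentions familiarization, so whether there is space must be checked on site.
3. **Records and analysis.** For any reused area, record that it was used and which cream came first. Keep the planned primary analysis and add a supportive model with visit and prior area use as terms. The split of 54 to 18 visit-2 observations as planned makes prior use hard to separate from visit; the constraint makes it 36 to 36. A yes/no term does not capture which cream came first, so report that descriptively.
4. **Text.** In Section 14, either limit the expectation of no additive effect explicitly to a single visit, or give a reason that also covers reuse between visits.
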